5.2.5 Efficacy Analysis

5.2.5.1 Primary endpoint analysis

Primary efficacy analysis

Descriptive statistics for (i) raw values at each time point and (ii) change from baseline to each time point in FVC [% predicted] will be computed by treatment group for the ATS analysis dataset (Statistical tables 14.2.1.1.1 and 14.2.1.2.1). The time variation in FVC [% predicted] will be modelled using a linear mixed effect model with random intercept, with raw values at each time point (from Week 4 to Week 28 included) in FVC [% predicted] as dependent variable (outcome), and stratum, treatment, time (continuous variable calculated as the actual number of days since baseline) and treatment by time interaction as explanatory variables (Statistical table 14.2.1.3.1).

The following statistical hypotheses will be tested:

- H0: Absence of difference between the treatment groups.
- H1: A difference exists between the treatment groups.

Least square means for FVC [% predicted] at each time-point (Statistical table 14.2.1.3.1, Figure 14.2.1.1), estimate of slopes, together with their 2-sided 90 and 95% confidence intervals will be presented for both treatment groups.

The comparison of PRM-151 with placebo will be carried out by

1. computing the estimate (estimate statement from SAS Proc MIXED) of the between group difference in change from baseline at week 28,
2. computing the corresponding 90% confidence interval
3. computing the p-value of the difference estimate compared to 0.

Statistical significance will be determined using a 2-sided type-one error rate of 0.10.

The listing of the estimates of the random parameters will be provided (Listing 16.2.6.9.1)

Due to the number of sites planned to recruit and randomize patients in the study, it is expected that each site will include too few patients to allow the inclusion of study site as a covariate in the analysis.

Sensitivity efficacy analysis on the Full Analysis Set population

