5.2.5.2 Secondary efficacy analyses

For all secondary efficacy endpoints, the analyses will be based on observed data only *i.e.*, no data will be imputed. All the following analyses will be performed on both the ATS and the PP analysis data set.

SO1: *To determine the effect size of PRM-151 relative to placebo in change from Baseline to Week 28 in normal lung parenchyma (normal + mild LAA) and interstitial lung abnormalities (ILA) as quantified on high-resolution CT (HRCT) imaging analysis, pooling subjects on a stable dose of pirfenidone or nintedanib with subjects not on other treatment for IPF.*

HRCT is performed at baseline and W28. Descriptive statistics will be computed by treatment group for baseline, week 28 and change from baseline to Week 28 in total lung volume and volume (in ml and % of total lung volume) of parenchyma features representative of normal lung (normal + mild LAA) and representative of interstitial lung abnormalities (ILA) as quantified by HRCT imaging (see section 8, Statistical table 14.2.6.1.1 and 14.2.6.2.2). A model similar to that of the primary analysis (see section 5.2.5.1) will be used to compare the two groups (Statistical tables 14.2.6.3.1 to 14.2.6.3.2, Figure 14.2.4.1 to 14.2.4.2). Individual's measurement of total lung volume and volume of parenchymal features quantified by HRCT imaging will be reported in Listing 16.2.6.3.

SO2: *To determine the effect size of PRM-151 relative to placebo in change from Baseline to Week 28 in mean FVC% predicted, separately in subjects on a stable dose of pirfenidone or nintedanib and in subjects not on other treatments for IPF.*

The same model as the one for the primary analysis (see section 5.2.5.1) will be used for each subgroup (Statistical table 14.2.7.1.1 to 14.2.7.2.2, Figure 14.2.5.1.1 to 14.2.5.2.2). All measurements of FVC [% predicted] will be reported in Listing 16.2.6.1.1.

SO3: *To determine the effect size of PRM-151 relative to placebo in change from Baseline to Week 28 in normal lung (defined as normal + mild LAA) parenchyma and interstitial lung abnormalities (ILA) as quantified on HRCT imaging analysis, separately in subjects on a stable dose of pirfenidone or nintedanib and in subjects not on other treatments for IPF.*

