Descriptive statistics will be computed by treatment group and stratification level for week 0, week 28 and change from baseline to Week 28 in total lung volume and volume (in ml and % of total lung volume) of parenchyma features representative of normal (normal + mild LAA) lung and representative of interstitial lung abnormalities (ILA) as quantified by HRCT imaging (see section 8). A model similar to that of the primary analysis (see section 5.2.5.1) will be used to compare the two groups (Statistical table 14.2.8.1.1.1 to 14.2.8.2.3.2, Figure 14.2.6.1.1 to 14.2.6.2.2).

Individual's measurement of total lung volume and volumes of parenchymal features quantified by HRCT imaging will be reported in Listing 16.2.6.3.

SO4: To assess the tolerability and safety of PRM-151 in subjects with IPF through Week 28.

See Section 5.2.6 safety analysis.

SO5: To assess the ability of PRM-151 to reduce disease-related events associated with mortality

See Section 5.2.6 safety analysis.

SO6: To determine the effect size of PRM-151 relative to placebo on pulmonary function in addition to mean change in FVC% predicted

To determine the effect size of PRM-151 relative to placebo on pulmonary function, descriptive qualitative statistics and Odds-Ratios (PRM-151 /Placebo) with their 90% CIs will be calculated by treatment group and stratification level for:

- Subjects with a decline in FVC [% predicted] of $\geq 5\%$ and $\geq 10\%$ from baseline to week 28.
- Subjects with a decline in FVC [ml] of $\geq 100\text{ml}$ and $\geq 200\text{ml}$ from baseline to week 28.
- Subjects with an increase in FVC [% predicted] of $\geq 5\%$ and $\geq 10\%$ from baseline to week 28.
- Subjects with an increase in FVC [ml] of $\geq 100\text{ ml}$ and $\geq 200\text{ ml}$ from baseline to week 28.
- Subjects with stable disease by FVC [% predicted], defined as a change in FVC [% predicted] of $< 5\%$ from baseline to week 28.
- Subjects with stable disease by FVC in ml, defined as a change in FVC [ml] of $< 100\text{ml}$ from Baseline to week 28.

For each of these endpoints treatment groups will be compared using the Cochran-Mantel-Haenszel general association test available in the SAS Freq procedure, adjusting for the Stratum effect (Statistical table 14.2.9.1 to 14.2.9.2). Due to the small sample-size, the exact version of the test will be used. Odds ratio (with 90% CI) together with p-values will be reported.

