SO7: To determine the effect size of PRM-151 relative to placebo on 6-minute walking distance

The same descriptive statistics and analysis model as those of the primary analysis (see section 5.2.5.1) will be used (Statistical tables 14.2.10.1.1 to 14.2.10.3.2, Figure 14.2.7.1 to 14.2.7.2). All results of the 6-minute walk test will be reported in Listing 16.2.6.2.

SO8: To determine the effect size of PRM-151 relative to placebo on DLCO.

The same descriptive statistics and analysis model as those of the primary analysis (see section 5.2.5.1) will be used (Statistical tables 14.2.11.1.1 to 14.2.11.3.2, Figure 14.2.8.1 to 14.2.8.2). All DLCO measurements will be reported in Listing 16.2.6.1.2.

SO9: To determine the correlation between change in FVC [% predicted] and total lung volume and volume of ILA on HRCT from Baseline to Week 28

Correlation between change from baseline in FVC[% predicted] and (i) total lung volume (Statistical table 14.2.12.1.1 and 14.2.12.1.2, Figures 14.2.9.1.1 and 14.2.9.1.2) and (ii) volume of ILA on HRCT will be produced along with the corresponding scatter plots (Statistical table 14.2.12.2.1 and 14.2.12.2.2, Figures 14.2.9.2.1 and 14.2.9.2.2).

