6.2 Changes in secondary efficacy analyses

All secondary efficacy analyses will be performed on both the ATS and the PP.

To be consistent with the primary efficacy analysis, the same analysis model as those of the primary analysis (see section 5.2.5.1) will be used, instead of the ANOVA model initially planned, to determine the effect size of PRM-151 relative to placebo in change from Baseline to Week 28 in normal lung parenchyma (normal + mild LAA) and interstitial lung abnormalities (ILA) as quantified on high-resolution CT (HRCT) imaging analysis (SO1).

To be consistent with the primary efficacy analysis, the same descriptive statistics and analysis model as those of the primary analysis (see section 5.2.5.1) will be used, instead of the ANOVA model initially planned, to determine the effect size of PRM-151 relative to placebo in change from Baseline to Week 28 in mean FVC% predicted, separately in subjects on a stable dose of pirfenidone or nintedanib and in subjects not on other treatments for IPF (SO2).

To be consistent with the primary efficacy analysis, the same analysis model as those of the primary analysis (see section 5.2.5.1) will be used, instead of the ANOVA model initially planned, to determine the effect size of PRM-151 relative to placebo in change from Baseline to Week 28 in

normal lung (defined as normal + mild LAA) parenchyma and interstitial lung abnormalities (ILA) as quantified on HRCT imaging analysis (SO3).

Odds ratios will be computed in addition to quantitative statistics to determine (SO6) the effect size of PRM-151 relative to placebo on pulmonary function and mean change in FVC% predicted.

To be consistent with the primary efficacy analysis, the same descriptive statistics and analysis model as those of the primary analysis (see section 5.2.5.1) will be used to determine the effect size of PRM-151 relative to placebo on 6MWD (SO7) and DLCO (SO8).

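### DLCO and HRCT have one follow-up value but inherit the treatment-by-time model: as 5.2.5.1 is written a slope-based Week 28 change is unusable, and the sound contrast depends on a baseline role the SAP leaves in conflict

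*SAP*

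**What the plan says.** SAP 5.2.5.1 defines the primary model as a random-intercept linear mixed model "with raw values at each time point (from Week 4 to Week 28 included) in FVC [% predicted] as dependent variable (outcome"), with stratum, treatment, time in actual days since baseline, and treatment by time. It asks for "estimate of slopes, together with their 2-sided 90 and 95% confidence intervals" and for an estimate "of the between group difference in change from baseline at week 28". The contrast itself is not written out.

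That model is then carried over:
- **DLCO (SO8), 5.2.5.2:** "The same descriptive statistics and analysis model as those of the primary analysis (see section 5.2.5.1) will be used". SAP 6.2 repeats this.
- **HRCT (SO1, SO3), 5.2.5.2:** "A model similar to that of the primary analysis (see section 5.2.5.1) will be used to compare the two groups". SAP 6.2 is firmer and says "the same analysis model as those of the primary analysis (see section 5.2.5.1) will be used, instead of the ANOVA model initially planned".
- **HRCT subset in EO2, 5.2.5.3:** an approach similar to the primary analysis.

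On the schedule, the SAP states under SO1 that "HRCT is performed at baseline and W28". Protocol 7.10.1 places DLCO at Screening, Baseline and Week 28, and after that only in the extension. SAP 5.1 leaves extension data out.

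Baseline has three different roles. The model in 5.2.5.1 does not list it. SAP 5.3.1 makes it a covariate, but only in mixed models that pool the two strata. SAP 5.1.2 gives categorical time eight levels; there are seven post-baseline visits, so baseline would be an outcome row.

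**The concern.** With one value per patient near day 196, nothing in the design informs a slope. The time and treatment-by-time terms are identified only by how far Week 28 visits stray from day 196 and by any early End of Study values, which SAP 5.4.4 keeps. In the second case the slope largely compares patients who stopped early with those who completed. The fallback to categorical time in 5.1.2 does not help: with a single Week 28 level, treatment by time cannot be estimated.

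Baseline could rescue the model, but the SAP does not fix how it enters, and the sound contrast changes with that choice. By-stratum SO3 is the most exposed. It lies outside the 5.3.1 rule, yet SAP 9.1 lists least-squares means for change from baseline for it. A model without baseline can give a change only through the slope.

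SO1 is the first-listed secondary objective. A programmer who follows the text could produce either a sound estimate or a visibly unusable one. In the second case a model would probably have to be chosen after unblinding.

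**Working it through.** **Arm sizes.** The documents give no sample-size figure for DLCO or HRCT, so I use the primary calculation in SAP 2.3.2.
- Weighted difference: 0.75 × 2.25 + 0.25 × 3.75 = 2.625. SD 5, two-sided alpha 0.10, power 80%, 2:1.
- Placebo n = 1.5 × (1.645 + 0.842)² × 5² / 2.625² = 33.7, so 34, and 102 in total. The plan's figure is reproduced (power 0.804).
- For 68 v 34, √(1/68 + 1/34) = 0.210.

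**Slope against Week 28 difference, baseline not an outcome.** If every visit fell exactly on day 196, the design (intercept, treatment, day, treatment × day) would have rank 2 of 4, and the slope terms would not be estimable. Otherwise the ratio of SE(196 × interaction) to SE(treatment + 196 × interaction) is close to 196 / SD(days). It needs no outcome SD, so it holds for HRCT too, and it is the same with or without a baseline covariate.
- Whole days spread evenly over ±3: SD = √((7² − 1)/12) = 2, ratio 196/2 = 98 (simulation 99).
- A share p with an early value at Weeks 8 to 24 (mean 84 days early, mean square 84² + 1,568 = 8,624): variance = 4 + 8,624p − 7,056p². For p = 5%, 10%, 15% the SDs are 20.4, 28.2 and 33.7 days, and the ratios 9.6, 7.0 and 5.8. Simulated medians are 12, 7.2 and 5.8.
- Within SO3, simulated ratios at 5%, 10%, 15% are about 15, 7.4 and 5.9 (51 v 25) and 75, 22 and 7.7 (17 v 9, where placebo often has no early value). A second run of the small stratum gave 75, 18 and 8.2.

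The early shares are assumptions; the plan's 15% non-evaluability rate serves as the upper anchor.

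**DLCO illustration.** Protocol Table 1-1 (20 patients, Day 57) gives pooled SDs:
- baseline √((13 × 10.1² + 5 × 8.4²)/18) = 9.66;
- change √((13 × 4.9² + 5 × 2.1²)/18) = 4.31;
- implied correlation 1 − 4.31²/(2 × 9.66²) = 0.90.

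| Role of baseline | SE of 196 × interaction | SE of treatment + 196 × interaction |
|---|---|---|
| None | 21.04 × 9.66 = 203 (±3 days only) | 0.213 × 9.66 = 2.06; a raw level difference |
| Covariate | 89 (±3 days only); 11.0, 6.7, 5.5 at 5, 10, 15% early | 0.90; 0.95 at 15% early |
| Day-0 outcome row | 0.91 (0.210 × 4.31) | 2.03 (0.210 × 9.66); a raw level difference |

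The multipliers 21.04 and 0.213 are the simulated SEs in residual-SD units. With no baseline term and a true difference of 2 points, simulation gave 196 × interaction an SD of 203 and a rejection rate of 9.6% at the 10% level, which is no power.

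**Simple alternatives, Week 28 values only** (SE at 0, 5, 10, 15% missing): ANCOVA 0.89, 0.91, 0.93, 0.96; ANOVA on change 0.91, 0.93, 0.95, 0.98.

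**The case against.** The strongest reply is that the SAP can be read so that nothing fails. SAP 6.1 describes the model as drawing on every measurement up to Week 28, 5.1.2 has eight time levels, and the stated target is a change from baseline. If baseline is therefore a day-0 row, 196 × interaction is the right contrast and matches ANOVA on change. If 5.3.1 applies instead, the Week 28 difference meets the target. The numbered comparison steps in 5.2.5.1 do not name the slope, and *similar* in 5.2.5.2 leaves room to adapt for HRCT.

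Much of this stands, and it limits the point. A reader might infer that a slope-based change is unusable under every reading; the day-0 row shows otherwise. It does not remove the problem. SAP 5.2.5.1 restricts the outcome to Week 4 onwards, SO8 has no *similar*, 6.2 says *same* for HRCT, and no adapted model is written.

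Other inferences the documents do not support:
- **That the factor of 99 is the plan's figure.** It assumes an even ±3-day spread. Protocol 6.2 lets dosing slip by up to 2 weeks. If 10% to 50% of last doses slipped 1 to 14 days (assumed), the ratio would be about 60 to 38.
- **That inseparable random-intercept and residual variances spoil the treatment estimate.** They are inseparable only with one row per patient. Even then, three different splits of the variance gave the same estimate and SE.
- **That figure titles in 9.2 referring to each visit prove the model was left unadapted.** For HRCT the visits can simply be baseline and Week 28.

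**Conclusion.** The point holds conditionally. As 5.2.5.1 is written, with baseline outside the outcome, a slope-based Week 28 change for DLCO or HRCT has an SE about 6 to 99 times that of the Week 28 difference at 68 v 34, depending on the assumed day spread and early share. With baseline as a covariate, treatment + 196 × interaction is sound and the slope is not. With baseline as a day-0 outcome row, this reverses. The SAP supports both roles and also supports none, so the analysis is not fixed. By-stratum SO3 has no stated baseline term at all.

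Severity is low to moderate. These are secondary endpoints (plus the exploratory EO2 subset) without alpha control, and the sound readings agree closely (DLCO SE about 0.9 to 1.0). A reader might infer that the primary test or N = 102 is undermined. The single-follow-up problem does not reach them, since FVC is measured every 4 weeks. The conflict over baseline does sit in the primary model and should be settled there, but its effect on FVC is not sized here. The DLCO figures rest on small Phase 1 SDs at Day 57; the ratios do not use them.

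**What to change.** Before unblinding, for SO1, SO3, SO8 and the EO2 HRCT analyses:
- Use ANCOVA of change from baseline to Week 28 on treatment, baseline value and stratum (no stratum term within SO3), with no time terms or random intercept. Report the least-squares mean difference with its 90% CI.
- Acceptable alternatives are the protocol's ANOVA on change, or a two-time-point model with baseline as an outcome row and the contrast written out.
- Under ANCOVA or ANOVA, use Week 28 values in the main analysis and early End of Study values only as a sensitivity analysis.
- Align 5.1.2, 5.2.5.1, 5.2.5.2, 5.3.1 and 6.2 on one role for baseline, and extend 5.3.1 to by-stratum analyses. Keep the repeated-measures model for endpoints measured every 4 weeks.

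The cost is SAP wording; no new data are needed. Using Week 28 values alone raises the DLCO ANCOVA SE from 0.89 to 0.91–0.96 if 5% to 15% of patients lack one. ANCOVA gains little over ANOVA (0.89 v 0.91); the benefit is one defined, estimable model.

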6.3 Changes in exploratory efficacy analyses

All exploratory efficacy analysis will be performed on both the ATS and the PP.

It was initially planned (EO1) to evaluate the efficacy and estimate the size of effect of PRM-151 relative to placebo in change from baseline to weeks 4, 8, 12, 16, 20, and 24 in FVC % predicted, FVC in ml and 6 minute walking distance using mixed models with random intercepts. To obtain a better description of individual variability, both random intercepts and random slopes will be used.

The following not initially planned exploratory analysis were added (see section 5.2.5.3 for details):

- To assess the use of quantitative imaging in IPF (E03)
- To explore the relationship between Anti-Pentraxin 2 antibodies (ADA) presence and level of FVC [% predicted] in time
- To explore PK/PD relationship.
- To explore relationship between Pentraxin-2 levels and ADA
- To explore acute exacerbations
- To explore time variations in FVC % predicted separately in patient (i) on stable dose of pirfenidone and (ii) on a stable dose of pirfenidone.

7 Software documentation

All summaries and statistical analyses will be generated using SAS version 9.4 or higher.

8 Derived data

Derived variable	Derivation algorithm
Change from baseline to visit V (continuous)	Change from baseline of variable $X = X_{(Visit V)} - X_{(Baseline)}$ 
 ○ Negative values indicate a decrease in X ○ Positive values indicate an increase in X

Percent change from baseline to visit V (continuous)	Percent change from baseline of variable X= $100 * [X_{(Visit V)} - X_{(Baseline)}] / X_{(Baseline)}$ 
 ○ Negative values indicate a decrease in X ○ Positive values indicate an increase in X
Treatment compliance	Continuous variable: The compliance C_i for patient i will be computed according to: $C_i = \frac{D_i^t * 100}{D_i^p}$ 
where D_i^p mg is the total amount (mg) of IP prescribed to patient i and D_i^t is the total amount (mg) of IP actually taken by the patient during the study i.e., before the end of study for patient i.

Treatment compliance (categorical)	Categorical variable with three modalities: 
 • $C_i < 80\%$ • $80\% \leq C_i < 120\%$ • $C_i \geq 120\%$
Vital Sign abnormalities	
 • Heart rate: <50 or >90 • Respiratory rate: <12 or >20 • Body temperature: $<36.5^\circ\text{C}$ or $>37.5^\circ\text{C}$ • Diastolic Blood Pressure: <60 or >90 • Systolic Blood Pressure: <90 or >140 • Oxygen Saturation: <90
Event Duration	$(\text{End Date}) - (\text{Start Date}) + 1$
Total Lung Volume in ml (TLV)	Total lung volume (excluding vessel volume) in ml
Normal Lung Volume in ml (NLV)	NLV=Areas of Normal lung in ml + Mild Low Attenuation Area (LAA) in ml
% of Normal Lung Volume	$100 * (\text{NLV in ml}) / (\text{TLV in ml})$
% of mild Low Attenuation Areas (LAA)	$100 * (\text{mild LAA in ml}) / (\text{TLV in ml})$
% of moderate Low Attenuation Areas (LAA)	$100 * (\text{moderate LAA in ml}) / (\text{TLV in ml})$
% of severe Low Attenuation Areas (LAA)	$100 * (\text{severe LAA in ml}) / (\text{TLV in ml})$
% Ground Glass (GG)	$100 * (\text{GG in ml}) / (\text{TLV in ml})$

% Honeycombing (HC)	$100 * (\text{HC in ml}) / (\text{TLV in ml})$
% Reticular Changes (RC)	$100 * (\text{RC in ml}) / (\text{TLV in ml})$
Interstitial Lung Abnormalities (ILA) in ml	$(\text{ILA in ml}) = (\text{GG in ml}) + (\text{RC in ml}) + (\text{HC I ml})$
% Interstitial Lung Abnormalities (ILA)	$\% \text{ILA} = \% \text{GG} + \% \text{RC} + \% \text{HC}$
Historic FVC (% predicted)	$(\text{Historic FVC \% predicted}) = [\text{Historic FVC (mL)} / \text{Reference Result of FVC (mL) at baseline}] * 100$

9 Tables, Figures and Listings

9.1 List of tables

n°	Demographics and Baseline
14.1.1 to 14.1.3	Demographics (11.2)
14.1.2	Vital Signs at baseline
14.1.3	Physical examination at baseline
14.1.4	Hematology at baseline
14.1.5	Hematology abnormalities at baseline
14.1.6	Chemistry at baseline
14.1.7	Chemistry abnormalities at baseline
14.1.8	Coagulation at baseline
14.1.9	Coagulation abnormalities at baseline
14.1.10	Background therapy - use of nintedanib and pirfenidone prior to baseline
14.1.11.1.1 to 14.1.11.1.2	K-BILD Questionnaires at baseline
14.1.11.2.1 to 14.1.11.2.2	Leicester Cough Questionnaires at baseline
14.1.12.1 to 14.1.12.2	High Resolution Computed Tomography at Baseline
14.1.13.1 to 14.1.13.2	Pulmonary Function Tests at baseline
14.1.14.1 to 14.1.14.2	Six-minutes Walk Test at baseline
14.1.15.1 to 14.1.15.2	Pentraxin-2 levels at baseline
14.1.16.1 to 14.1.16.3	Anti-Pentraxin 2 antibodies (ADA) at baseline
14.1.17.1 to 14.1.17.3	Baseline Genetic Status
14.1.18.1 to 14.1.18.3	Biomarker levels at baseline
14.1.19	Disposition of patients (10.1)
14.1.20	Datasets analyzed (11.1)
14.1.21	Reasons for exclusion from the ATS
14.1.22	Reasons for exclusion from the PP
14.1.23	Reasons for study discontinuations
14.1.24	Major protocol deviations (10.2)
14.1.25	Minor protocol deviations (10.2)
14.1.26.1 to 14.1.26.2	Past medical history
14.1.27.1 to 14.1.27.2	Current medical history

14.1.28.1 to 14.1.28.2	Previous therapy for IPF
14.1.29.1 to 14.1.29.2	Current therapy for IPF
14.1.30.1 to 14.1.30.2	Previous other therapy
14.1.31.1 to 14.1.31.2	Current other therapy
14.1.32.1 to 14.1.32.2	Treatment compliance (11.3)
n°	Efficacy Results
14.2.1.1.1 to 14.2.1.1.3	(PO1) Forced Vital Capacity (% predicted FVC) - raw values at each visit
14.2.1.2.1 to 14.2.1.2.3	(PO1) Forced Vital Capacity (% predicted FVC) - change from baseline to each visit
14.2.1.3.1.a to 14.2.1.3.3.a	(PO1) Forced Vital Capacity (% predicted FVC): Anova table
14.2.1.3.1.b to 14.2.1.3.3.b	(PO1) Forced Vital Capacity (% predicted FVC): Model parameter estimates
14.2.1.3.1.c to 14.2.1.3.3.c	(PO1) Forced Vital Capacity (% predicted FVC): Least Square Means by stratum at each visit
14.2.1.3.1.d to 14.2.1.3.3.d	(PO1) Forced Vital Capacity (% predicted FVC): Least Square Means for Change from baseline at each visit
14.2.2.1.a	(PO1) Sensitivity Analysis: Forced Vital Capacity (% predicted FVC) - raw values by visit and stratum - No Background Therapy
14.2.2.1.b	(PO1) Sensitivity Analysis: Forced Vital Capacity (% predicted FVC) - raw values by visit and stratum - Pirfenidone or Nintedanib
14.2.2.2.a	(PO1) Sensitivity Analysis: Forced Vital Capacity (% predicted FVC) - change from baseline to each visit by stratum - No Background Therapy
14.2.2.2.b	(PO1) Sensitivity Analysis: Forced Vital Capacity (% predicted FVC) - change from baseline to each visit by stratum - Pirfenidone or Nintedanib
14.2.2.3.a	(PO1) Sensitivity Analysis: Forced Vital Capacity (% predicted FVC) - Stratum Interaction - Anova table
14.2.2.3.b	(PO1) Sensitivity Analysis: Forced Vital Capacity (% predicted FVC) - Stratum Interaction- Model parameter estimates
14.2.2.3.c	(PO1) Sensitivity Analysis: Forced Vital Capacity (% predicted FVC) - Stratum Interaction- Least Square Means by stratum at each visit
14.2.2.3.d	(PO1) Sensitivity Analysis: Forced Vital Capacity (% predicted FVC) - Stratum Interaction- Least Square Means by stratum for change from baseline at each visit
14.2.3.a	(PO1) Sensitivity Analysis: Forced Vital Capacity (% predicted FVC) - Without adjusting on stratum - Anova table
14.2.3.b	(PO1) Sensitivity Analysis: Forced Vital Capacity (% predicted FVC) - Without adjusting on stratum - Model parameter estimates
14.2.3.c	(PO1) Sensitivity Analysis: Forced Vital Capacity (% predicted FVC) - Without adjusting on stratum - Least Square Means at each visit

14.2.3.d	(PO1) Sensitivity Analysis: Forced Vital Capacity (% predicted FVC) - Without adjusting on stratum - Least Square Means for Change from baseline at each visit
14.2.4.1.1 to 14.2.4.1.18	(PO1) Sensitivity analysis: Forced Vital Capacity (% predicted FVC) - raw values at each visit by site
14.2.4.2.1 to 14.2.4.2.18	(PO1) Sensitivity analysis: Forced Vital Capacity (% predicted FVC) - change from baseline to each visit by site
14.2.5.1.1 to 14.2.5.1.2	(PO1) Sensitivity Analysis: Forced Vital Capacity (% predicted FVC) - Initially planned analysis - Model parameter estimates
14.2.5.2.1 to 14.2.5.2.2	(PO1) Sensitivity Analysis: Forced Vital Capacity (% predicted FVC) - Initially planned analysis - Least Square Means by stratum for change from baseline at each visit
14.2.6.1.1 to 14.2.6.1.2	(SO1) Secondary Efficacy Analysis: HRCT imaging analysis - raw value at each visit
14.2.6.2.1 to 14.2.6.2.2	(SO1) Secondary Efficacy Analysis: HRCT imaging analysis - change from baseline
14.2.6.3.1.a to 14.2.6.3.2.a	(SO1) Secondary Efficacy Analysis: HRCT imaging analysis - Anova table
14.2.6.3.1.b to 14.2.6.3.2.b	(SO1) Secondary Efficacy Analysis: HRCT imaging analysis - Model parameter estimates
14.2.6.3.1.c to 14.2.6.3.2.c	(SO1) Secondary Efficacy Analysis: HRCT imaging analysis - Least Square Means by stratum for change from baseline
14.2.7.1.1.a to 14.2.7.1.2.a	(SO2) Secondary Efficacy Analysis: Forced Vital Capacity (% predicted FVC) - Separately for each stratum - Anova table - No Background Therapy
14.2.7.1.1.b to 14.2.7.1.2.b	(SO2) Secondary Efficacy Analysis: Forced Vital Capacity (% predicted FVC) - Separately for each stratum - Model parameter estimates - No Background Therapy
14.2.7.1.1.c to 14.2.7.1.2.c	(SO2) Secondary Efficacy Analysis: Forced Vital Capacity (% predicted FVC) - Separately for each stratum - Least Square Means at each visit - No Background Therapy
14.2.7.1.1.d to 14.2.7.1.2.d	(SO2) Secondary Efficacy Analysis: Forced Vital Capacity (% predicted FVC) - Separately for each stratum - Least Square Means for change from baseline at each visit - No Background Therapy
14.2.7.2.1.a to 14.2.7.2.2.a	(SO2) Secondary Efficacy Analysis: Forced Vital Capacity (% predicted FVC) - Separately for each stratum - Anova table - Pirfenidone or Nintedanib
14.2.7.2.1.b to 14.2.7.2.2.b	(SO2) Secondary Efficacy Analysis: Forced Vital Capacity (% predicted FVC) - Separately for each stratum - Model parameter estimates - Pirfenidone or Nintedanib
14.2.7.2.1.c to 14.2.7.2.2.c	(SO2) Secondary Efficacy Analysis: Forced Vital Capacity (% predicted FVC) - Separately for each stratum - Least Square Means at each visit - Pirfenidone or Nintedanib
14.2.7.2.1.d to 14.2.7.2.2.d	(SO2) Secondary Efficacy Analysis: Forced Vital Capacity (% predicted FVC) - Separately for each stratum - Least Square Means for change from baseline at each visit - Pirfenidone or Nintedanib
14.2.8.1.1.1 to 14.2.8.1.1.2	(SO3) Secondary Efficacy Analysis: HRCT imaging analysis - Separately for each stratum - raw values at each stratum- No Background Therapy
14.2.8.1.2.1 to 14.2.8.1.2.2	(SO3) Secondary Efficacy Analysis: HRCT imaging analysis - Separately for each stratum - Change from baseline- No Background Therapy
14.2.8.1.3.1.a to 14.2.8.1.3.2.a	(SO3) Secondary Efficacy Analysis: HRCT imaging analysis - Separately for each stratum - Anova table - No Background Therapy

14.2.8.1.3.1.b to 14.2.8.1.3.2.b	(SO3) Secondary Efficacy Analysis: HRCT imaging analysis - Separately for each stratum - Model parameter estimates - No Background Therapy
14.2.8.1.3.1.c to 14.2.8.1.3.2.c	(SO3) Secondary Efficacy Analysis: HRCT imaging analysis - Separately for each stratum - Least Square Means for change from baseline- No Background Therapy
14.2.8.2.1.1 to 14.2.8.2.1.2	(SO3) Secondary Efficacy Analysis: HRCT imaging analysis - Separately for each stratum - raw values at each stratum - Pirfenidone or Nintedanib
14.2.8.2.2.1 to 14.2.8.2.2.2	(SO3) Secondary Efficacy Analysis: HRCT imaging analysis - Separately for each stratum - Change from baseline - Pirfenidone or Nintedanib
14.2.8.2.3.1.a to 14.2.8.2.3.2.a	(SO3) Secondary Efficacy Analysis: HRCT imaging analysis - Separately for each stratum - Anova table - Pirfenidone or Nintedanib
14.2.8.2.3.1.b to 14.2.8.2.3.2.b	(SO3) Secondary Efficacy Analysis: HRCT imaging analysis - Separately for each stratum - Model parameter estimates - Pirfenidone or Nintedanib
14.2.8.2.3.1.c to 14.2.8.2.3.2.c	(SO3) Secondary Efficacy Analysis: HRCT imaging analysis - Separately for each stratum - Least Square Means for change from baseline - Pirfenidone or Nintedanib
14.2.9.1.a to 14.2.9.2.a	(SO6) Secondary analyses: Effect size in PRM-151 - Treatment Effect
14.2.9.1.b to 14.2.9.2.b	(SO6) Secondary analyses: Effect size in PRM-151 - Common Odds Ratio
14.2.10.1.1 to 14.2.10.1.2	(SO7) Secondary Efficacy Analysis: 6 Minute Walk Distance - raw values at each visit
14.2.10.2.1 to 14.2.10.2.2	(SO7) Secondary Efficacy Analysis: 6 Minute Walk Distance - change from baseline to each visit
14.2.10.3.1a to 14.2.10.3.2a	(SO7) Secondary Efficacy Analysis: 6 Minute Walk Distance - Anova table
14.2.10.3.1b to 14.2.10.3.2b	(SO7) Secondary Efficacy Analysis: 6 Minute Walk Distance - Model parameter estimates
14.2.10.3.1c to 14.2.10.3.2c	(SO7) Secondary Efficacy Analysis: 6 Minute Walk Distance - Least Square Means by stratum at each visit
14.2.10.3.1d to 14.2.10.3.2d	(SO7) Secondary Efficacy Analysis: 6 Minute Walk Distance - Least Square Means for Change from baseline at each visit
14.2.11.1.1 to 14.2.11.1.2	(SO8) Secondary Efficacy Analysis: DLCO - raw values at each visit
14.2.11.2.1 to 14.2.11.2.2	(SO8) Secondary Efficacy Analysis: DLCO - change from baseline
14.2.11.3.1a to 14.2.11.3.2a	(SO8) Secondary Efficacy Analysis: DLCO - Anova table
14.2.11.3.1b to 14.2.11.3.2b	(SO8) Secondary Efficacy Analysis: DLCO - Model parameter estimates
14.2.11.3.1c to 14.2.11.3.2c	(SO8) Secondary Efficacy Analysis: DLCO - Least Square Means by stratum for change from baseline
14.2.12.1.1 to 14.2.12.1.2	(SO9) Secondary Efficacy Analysis: Correlation between Forced Vital Capacity (% predicted FVC) and total lung volume
14.2.12.2.1 to 14.2.12.2.2	(SO9) Secondary Efficacy Analysis: Correlation between Forced Vital Capacity (% predicted FVC) and volume of ILA on HRCT
14.2.13.1.a to 14.2.13.2.a	(EO1) Exploratory analyses: FV [%predicted] - Random Slope Analysis - Anova table
14.2.13.1.b to 14.2.13.2.b	(EO1) Exploratory analyses: FV [%predicted] - Random Slope Analysis- Model parameter estimates

14.2.13.1.c to 14.2.13.2.c	(EO1) Exploratory analyses: FV [%predicted] - Random Slope Analysis- Least Square Means by stratum at each visit
14.2.13.1.d to 14.2.13.2.d	(EO1) Exploratory analyses: FV [%predicted] - Random Slope Analysis- Least Square Means for change from baseline at each visit
14.2.14.1.1.a to 14.2.14.1.2.a	(EO1) Exploratory analyses: FV [%predicted] - Random Slope Analysis Separately for each stratum - Anova table - No Background Therapy
14.2.14.1.1.b to 14.2.14.1.2.b	(EO1) Exploratory analyses: FV [%predicted] - Random Slope Analysis Separately for each stratum - Model parameter estimates - No Background Therapy
14.2.14.1.1.c to 14.2.14.1.2.c	(EO1) Exploratory analyses: FV [%predicted] - Random Slope Analysis Separately for each stratum - Least Square Means at each visit - No Background Therapy
14.2.14.1.1.d to 14.2.14.1.2.d	(EO1) Exploratory analyses: FV [%predicted] - Random Slope Analysis Separately for each stratum - Least Square Means for change from baseline at each visit - No Background Therapy
14.2.14.2.1.a to 14.2.14.2.2.a	(EO1) Exploratory analyses: FV [%predicted] - Random Slope Analysis Separately for each stratum - Anova table - Pirfenidone or Nintedanib
14.2.14.2.1.b to 14.2.14.2.2.b	(EO1) Exploratory analyses: FV [%predicted] - Random Slope Analysis Separately for each stratum - Model parameter estimates - Pirfenidone or Nintedanib
14.2.14.2.1.c to 14.2.14.2.2.c	(EO1) Exploratory analyses: FV [%predicted] - Random Slope Analysis Separately for each stratum - Least Square Means at each visit- Pirfenidone or Nintedanib
14.2.14.2.1.d to 14.2.14.2.2.d	(EO1) Exploratory analyses: FV [%predicted] - Random Slope Analysis Separately for each stratum - Least Square Means for change from baseline at each visit - Pirfenidone or Nintedanib
14.2.15.1.1 to 14.2.15.1.2	(EO1) Exploratory analyses: FV [ml] - Random Slope Analysis - Raw Values at Each Visit
14.2.15.1.2 to 14.2.15.2.2	(EO1) Exploratory analyses: FV [ml] - Random Slope Analysis - Change from baseline at each visit
14.2.15.3.1.a to 14.2.15.3.2.a	(EO1) Exploratory analyses: FV [ml] - Random Slope Analysis - Anova table
14.2.15.3.1.b to 14.2.15.3.2.b	(EO1) Exploratory analyses: FV [ml] - Random Slope Analysis- Model parameter estimates
14.2.15.3.1.c to 14.2.15.3.2.c	(EO1) Exploratory analyses: FV [ml] - Random Slope Analysis- Least Square Means by stratum at each visit
14.2.15.3.1.d to 14.2.15.3.2.d	(EO1) Exploratory analyses: FV [ml] - Random Slope Analysis- Least Square Means for change from baseline at each visit
14.2.16.1.1.1 to 14.2.16.1.1.2	(EO1) Exploratory analyses: FV [ml] - Random Slope Analysis Separately for each stratum - Raw values at each visit - No Background Therapy
14.2.16.1.2.1 to 14.2.16.1.2.2	(EO1) Exploratory analyses: FV [ml] - Random Slope Analysis Separately for each stratum - Change from baseline to eah visit - No Background Therapy
14.2.16.1.3.1.a to 14.2.16.1.3.2.a	(EO1) Exploratory analyses: FV [ml] - Random Slope Analysis Separately for each stratum - Anova table - No Background Therapy
14.2.16.1.3.1.b to 14.2.16.1.3.2.b	(EO1) Exploratory analyses: FV [ml] - Random Slope Analysis Separately for each stratum - Model parameter estimates - No Background Therapy
14.2.16.1.3.1.c to 14.2.16.1.3.2.c	(EO1) Exploratory analyses: FV [ml] - Random Slope Analysis Separately for each stratum - Least Square Means at each visit - No Background Therapy
14.2.16.1.3.1.d to 14.2.16.1.3.2.d	(EO1) Exploratory analyses: FV [ml] - Random Slope Analysis Separately for each stratum - Least Square Means for change from baseline at each visit - No Background Therapy

14.2.16.2.1.1 to 14.2.16.2.1.2	(EO1) Exploratory analyses: FV [ml] - Random Slope Analysis Separately for each stratum - Raw values at each visit - Pirfenidone or Nintedanib
14.2.16.2.2.1 to 14.2.16.2.2.2	(EO1) Exploratory analyses: FV [ml] - Random Slope Analysis Separately for each stratum - Change from baseline to each visit - Pirfenidone or Nintedanib
14.2.16.2.3.1.a to 14.2.16.2.3.2.a	(EO1) Exploratory analyses: FV [ml] - Random Slope Analysis Separately for each stratum - Anova table - Pirfenidone or Nintedanib
14.2.16.2.3.1.b to 14.2.16.2.3.2.b	(EO1) Exploratory analyses: FV [ml] - Random Slope Analysis Separately for each stratum - Model parameter estimates - Pirfenidone or Nintedanib
14.2.16.2.3.1.c to 14.2.16.2.3.2.c	(EO1) Exploratory analyses: FV [ml] - Random Slope Analysis Separately for each stratum - Least Square Means at each visit- Pirfenidone or Nintedanib
14.2.16.2.3.1.d to 14.2.16.2.3.2.d	(EO1) Exploratory analyses: FV [ml] - Random Slope Analysis Separately for each stratum - Least Square Means for change from baseline at each visit - Pirfenidone or Nintedanib
14.2.17.1.a to 14.2.17.2.a	(EO1) Exploratory analyses:6-Minute Walk distance - Random Slope Analysis - Anova table
14.2.17.1.b to 14.2.17.2.b	(EO1) Exploratory analyses:6-Minute Walk distance - Random Slope Analysis- Model parameter estimates
14.2.17.1.c to 14.2.17.2.c	(EO1) Exploratory analyses:6-Minute Walk distance - Random Slope Analysis- Least Square Means by stratum at each visit
14.2.17.1.d to 14.2.17.2.d	(EO1) Exploratory analyses:6-Minute Walk distance - Random Slope Analysis- Least Square Means for change from baseline at each visit
14.2.18.1.1.1 to 14.2.18.1.1.2	(EO1) Exploratory analyses:6-Minute Walk distance - Random Slope Analysis Separately for each stratum - Raw values at each visit - No Background Therapy
14.2.18.1.2.1 to 14.2.18.1.2.2	(EO1) Exploratory analyses:6-Minute Walk distance - Random Slope Analysis Separately for each stratum - Change from Baseline to each visit - No Background Therapy
14.2.18.1.3.1.a to 14.2.18.1.3.2.a	(EO1) Exploratory analyses:6-Minute Walk distance - Random Slope Analysis Separately for each stratum - Anova table - No Background Therapy
14.2.18.1.3.1.b to 14.2.18.1.3.2.b	(EO1) Exploratory analyses:6-Minute Walk distance - Random Slope Analysis Separately for each stratum - Model parameter estimates - No Background Therapy
14.2.18.1.3.1.c to 14.2.18.1.3.2.c	(EO1) Exploratory analyses:6-Minute Walk distance - Random Slope Analysis Separately for each stratum - Least Square Means at each visit - No Background Therapy
14.2.18.1.3.1.d to 14.2.18.1.3.2.d	(EO1) Exploratory analyses:6-Minute Walk distance - Random Slope Analysis Separately for each stratum - Least Square Means for change from baseline at each visit - No Background Therapy
